2.8.2.1 Expert Consultation

Objective: To elicit experts' opinions on assessing and managing psychological adaptation challenges of parent caregivers of children with leukemia.

Method: Expert consultation will analyse the implementation methods of existing psychosocial management trials for parent caregivers in pediatric oncology settings.

Analysis: We will utilise an expert forum to gather insights on the application of selected published protocols for psychosocial interventions in parent caregivers of children with cancer. The study team will select trials based on rigorous methodology, such as randomised, fully powered, rater-blinded, and placebo-controlled efficacy trials focusing on parent caregiver adaptation and adherence to MRC Guidance on complex interventions in hospital or home-based settings.

Further, the experts will be requested to evaluate the available possibilities and choose the most appropriate approach for implementing our stage-matched communication and adaptation intervention. The options appraisal will employ the TOWS approach(Chopra et al., 2025). This tool functions as a decision-support framework, using a matrix to systematically compare and evaluate external threats ("T") and opportunities ("O") against the internal strengths ("S") and weaknesses ("W") of the study team's capabilities. The matrix will draw upon the various methodologies utilized throughout the trials. The results generated by this decision-making tool will guide the selection of the implementation model for the upcoming stage-specific support trial.

2.8.2.2 Professionals' Semi-Structured Interviews

Objective: To determine the psychological adaptation needs of parent caregivers of children with leukemia from the professionals' perspective.

Method: A variety of pertinent specialists, both clinical and academic, will participate in semi-structured interviews to explore the psychological adaptation difficulties that parent caregivers of children with leukemia encounter. The structure of the interviews will be similar to parent caregiver interviews.

Participants: Pediatric oncologists, clinical psychologists, psychiatric social workers, pediatric oncology nurses, and community health workers will be interviewed.

Analysis: Transcribed interviews from all participants will be analysed with Nvivo(Dhakal, n.d.) and be subjected to thematic analysis(Braun and Clarke, 2006).

2.9 Stage 3: Model Stage-Matched Intervention Refinement in to a Draft

The components of the intervention model, developed based on insights collected in Stages 1 and 2, will be further refined for clarity and effectiveness. The model will be sent to expert professionals for their recommendations and corrections. This will include semi-directed focus groups with parent caregivers and a Delphi with relevant professionals. During each study activity, we will present the details of the model intervention and ask in-depth questions to gather perspectives and feedback on the practicality, acceptability, and how tolerable each aspect of the model intervention is.

2.9.1 Focus Group and Delphi process

Objective: To identify means of intervention application and the contents of the model from the perspectives of parent caregivers of children with leukemia, and experts.

Method: We will organize focus groups, each lasting 1 to 2 hours, with parents caring for children with leukemia. During these sessions, the intervention model developed from available resources and insights gathered in earlier stages, will be reviewed. The focus groups will evaluate the materials in terms of their effectiveness, usability, and capacity to support the psychological adaptation of parent caregivers. In parallel, experts will provide ratings and feedback on the model through an e-Delphi process.

Participants: Focus groups will consist of eight participants per group (parent caregivers of children with leukemia) per facility. Delphi will consist of multidisciplinary experts (approximately 8–10 members) across the various disciplines.

Analysis: Transcription and thematic analysis will be applied to the conversations. the degree of concentration and coordination of experts' opinions will be analysed through Delphi process.

2.10 Stage 4: Pilot Trial of the Stage-Matched Intervention Draft

The last stage of the program involves testing the stage-matched psychological adaptation intervention with a population representing the participants expected to participate in a large-scale randomised controlled trial if the pilot trial produces positive productive result results. This stage is only described briefly; although the detailed procedure will be described in a protocol for the pilot trial.

Objective: The pilot trial aims to:

1. Evaluate the feasibility of the stage-matched psychological adaptation intervention among parent caregivers of children with leukemia and the acceptability of the intervention by participants.
2. Preliminarily investigate the efficacy of the intervention in improving psychological adaptation, coping, and reducing distress in parent caregivers.
3. Examine the acceptability of the stage-matched psychological adaptation intervention among parent caregivers of children with leukemia.

Method: This study will use a two-arm pilot randomized controlled trial design involving parent caregivers of children with leukemia in two facilities of a tertiary care hospital in Pakistan. To simplify implementation and minimize contamination, each facility will be randomly assigned to either the intervention or control group.

The intervention group will receive stage-matched psychological adaptation program alongside routine medical care, while the control group will continue with standard routine medical care. Cluster randomization at the facility level is employed to prevent potential spillover effects that could occur with individual randomization within the same setting. This approach reflects real-world practice, where interventions are typically implemented at the organizational level across entire facilities rather than targeting individual participants. Using cluster randomization also enhances intervention fidelity by allowing consistent delivery and standardized staff training within each facility. Moreover, it aligns the study design with practical implementation

conditions by accounting for variations in resources, workflows, and procedures across different facilities.

Participants: Parent caregivers (biological parents or step-parents of children diagnosed with leukemia. Participants who plan to relocate outside the study area during the study period will be excluded. The sample size estimation was initially derived using individual-level power calculations.

Sample size: The sample size was selected to (1) provide precise estimates of key feasibility parameters (e.g., recruitment rate, retention, adherence), (2) align with published pilot trial recommendations (Ying et al., 2025), and (3) reflect sample sizes used in comparable psychosocial intervention pilots in pediatric oncology settings (Koyu and Kilcarslan, 2024). We aim to recruit $N = 70$ parent caregivers (35 per arm). This sample size allows estimation of a 75% retention rate with a 95% confidence interval width of $\pm 13\%$. Accounting for an anticipated 25% attrition rate common in LMIC psychosocial trials, we will recruit up to 88 participants. This sample is sufficient to assess feasibility, acceptability, and preliminary effects, while informing sample size calculations for a future definitive RCT.

Setting: The study will be conducted in a tertiary care hospital in Pakistan providing pediatric oncology services.

Study procedures: The study will be conducted over 12 weeks, with interventions delivered by trained mental health professionals and outcome assessments carried out by research assistants. After recruitment, participants will provide informed consent and be screened for eligibility. Caregivers in the intervention group will receive a stage-matched psychological adaptation program based on the transactional family adaptation model and culturally adapted coping strategies. The final intervention protocol will be developed after the initial three stages.

Outcome evaluations will be conducted at baseline, mid-intervention, and post-intervention to assess feasibility, acceptability, adherence, and effectiveness, using methods such as diaries, observations, and satisfaction measures. At the end of the study, caregivers will participate in semi-structured interviews and complete questionnaires to evaluate outcomes. Additionally, professionals delivering the intervention will be interviewed to identify strengths of the trial and assessment methods. Key outcomes include improved psychological adaptation, reduced distress,

enhanced coping skills, and better quality of life among caregivers. Figure 4 summarizes the whole procedure for the pilot RCT.

[figure not shown]

Figure 3 Flowchart of pilot RCT of stage matched intervention draft

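### The ±13% precision quoted for a 75% retention rate does not match the sample size it is attached to: it is about ±10 points for N = 70 and ±14 points for 35 per arm

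*Protocol*

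**What the plan says.** The sample-size paragraph of section 2.10 gives the target first: "We aim to recruit $N = 70$ parent caregivers (35 per arm"). The next sentence is "This sample size allows estimation of a 75% retention rate with a 95% confidence interval width of" ±13%. Only after that is the number raised: "Accounting for an anticipated 25% attrition rate common in LMIC psychosocial trials, we will recruit up to 88 participants". Just before this paragraph the basis is described: "The sample size estimation was initially derived using individual-level power calculations". No interval method, intraclass correlation or design effect is given.

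The same section sets the allocation: "each facility will be randomly assigned to either the intervention or control group". There are two facilities, and the Limitations confirm one per arm. Table 3 gives a different pilot size, 34 caregivers from each facility (68 in total), and the abstract gives 88.

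**The concern.** In the order of the text, the sample size that the precision sentence refers to can only be 70, or 35 per arm, because 88 has not yet appeared. A 95% interval around 75% is a one-line calculation, and ±13 is neither the answer for 70 nor the answer for 35.

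Precise estimation of feasibility parameters is the first of three reasons that section 2.10 gives for the sample size. Retention is the only such parameter given a precision. As written, a reader cannot tell how many people the figure rests on or whether it describes the whole sample or one facility. A definitive trial planned from this pilot could carry the figure forward.

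**Working it through.** **Inputs.** Retention p = 0.75, confidence level 95%, stated precision ±13%, N = 70 and 35 per arm, ceiling 88: all from section 2.10. The 34 per facility and 68 in total are from Table 3. An even split of 88 gives 44 per facility; the protocol does not state 44. The ± sign means that 13 is read as a half-width.

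**Trying to reproduce the stated figure.** Half-width = 1.96 × √(p(1 − p)/n), with p(1 − p) = 0.75 × 0.25 = 0.1875.

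- n = 70: 1.96 × √(0.1875/70) = 1.96 × 0.05175 = 0.101, or ±10.1 points.
- n = 35: 1.96 × √(0.1875/35) = 1.96 × 0.07319 = 0.143, or ±14.3 points.

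The stated ±13 is not reproduced. The same formula at every size in play gives:

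| n | Where it comes from | 95% half-width, points |
|---|---|---|
| 34 | per facility, Table 3 | 14.6 |
| 35 | per arm, section 2.10 | 14.3 |
| 44 | half of 88 | 12.8 |
| 68 | total, Table 3 | 10.3 |
| 70 | total, section 2.10 | 10.1 |
| 88 | ceiling, section 2.10 | 9.0 |

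**Does another interval method give ±13?** Half-widths in points, evaluated at exactly 75%:

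| Method | n = 70 | n = 35 |
|---|---|---|
| Simple (Wald) | 10.1 | 14.3 |
| Continuity-corrected | 10.9 | 15.8 |
| Wilson | 10.0 | 13.8 |
| Agresti-Coull | 10.0 | 14.0 |
| Jeffreys | 10.0 | 13.9 |
| Clopper-Pearson | 10.7 | 15.3 |

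None rounds to 13. The upper limit of the Clopper-Pearson interval at n = 35 does lie 13.0 points above 75%, but its lower limit lies 17.5 points below, so that is not a ±13 interval.

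**Which n would give ±13?** n = 1.96² × 0.1875/0.13² = 0.7203/0.0169 = 42.6, so 43. Any n from 40 to 46 rounds to ±13 by this formula. The matching n is about 40 with Wilson and about 48 with Clopper-Pearson.

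**Other routes.**

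- If 13 points were the full width, n = 0.7203/0.065² = 170.5, so 171 people would be needed.
- A 99% interval at N = 70 gives ±13.3, but the text says 95%.
- A design effect of (0.13/0.1014)² = 1.64 at N = 70 would give ±13. With 35 per facility that is an intraclass correlation of 0.64/34, about 0.019. None is stated, and the described basis is individual-level.

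**Size of the discrepancy.** Overall, 13 − 10.1 = 2.9 points too wide. Per arm, 14.3 − 13 = 1.3 points too narrow.

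**The case against.** The strongest reply is that little depends on the figure. Section 2.10 lists retention as one of three example feasibility parameters and nowhere calls it the main one. Section 2.10.1 rests progression on a process evaluation and participant feedback, with no retention threshold. For the pooled sample the error is conservative, since the true simple precision is better than stated. All of this stands, and it limits the weight of the point. It does not make the number right. Nor does the promise in section 2.10 of a later pilot protocol cure a figure already stated here.

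Three stronger readings are tempting, and the documents do not support them.

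- **That ±13 was computed on one arm of 88.** The match at 44 (±12.8) is close, but the protocol does not say so, and the n that fits ±13 runs from about 40 to 48 depending on the method.
- **That the retention denominator is wrong.** Read literally, 70 is a number to be recruited, which is a proper denominator for retention. The text leaves it unclear whether 70 means recruited or completing; it does not show an error of denominator.
- **That clustering makes the true precision a specific wider figure.** The design is clustered ("Cluster randomization at the facility level is employed to prevent potential spillover effects"), and an individual-level interval leaves out between-facility variation. But the protocol gives no intraclass correlation, and with one facility per arm it cannot be separated from the arm effect. A range built on assumed values would replace one unsupported figure with another. The Limitations already acknowledge the two-cluster constraint for hypothesis testing. A figure conditional on these two facilities is acceptable in a pilot if it is labelled as such.

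**Conclusion.** The point holds as an arithmetic error of modest size. At 75% retention, the stated 95% precision is wrong for the sample size it is attached to, whether that is read as the total or as one arm, and under each standard interval method tried. The conclusion assumes only that ± denotes a half-width, that the level is 95% as stated, and that the sample size meant is the 70 (35 per arm) in the preceding sentence. Substituting the 68 from Table 3 does not rescue it (±10.3 overall, ±14.6 per facility).

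A reader might infer that the pilot is too small or that a progression decision is compromised. Neither follows: no decision rule in the protocol uses ±13, and the error does not change the design. It deserves correction because it is the only precision figure behind the sample size and is cheap to put right.

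**What to change.** First reconcile the pilot size across Table 3 (68), the section 2.10 target (70) and the ceiling of 88 in section 2.10 and the abstract. Then replace the precision sentence with one that names the number enrolled, the interval method, all enrolled caregivers as the denominator, and whether the figure is overall or per facility. By the simple formula the values are:

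- 70 enrolled: ±10.1 points overall and ±14.3 per facility of 35.
- 88 enrolled: ±9.0 points overall and ±12.8 per facility of 44, if split evenly.

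Add that the figure is conditional on these two facilities and does not include between-facility variation, and report retention by facility. Do not write a range based on an assumed intraclass correlation into the protocol.

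The cost is a short rewrite in section 2.10 plus the reconciliation of the sample sizes. Correcting the precision requires no change in N. The only downside is that, if 35 per arm is kept, the per-facility figure is slightly less favourable than the ±13 now stated.

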Study Title:

Development of a stage matched psychosocial intervention to enhance psychological adaptation among parent caregivers of children with leukemia in Pakistan: a study protocol

NCT Number:

Not Registered Yet

(The NCT number will be added once the study is registered on [ClinicalTrials.gov](https://clinicaltrials.gov).)

Start Date:

June, 2025

Completion Date:

December, 2026

Development of a stage matched psychosocial intervention to enhance psychological adaptation among parent caregivers of children with leukemia in Pakistan: a study protocol

Abstract

Purpose: To develop a structured, systematic and cultural adapted stage-matched psychosocial intervention to improve psychological adaptation in parent caregivers of children with leukemia in Pakistan.

Methods: This protocol study adopts a multi-stage approach guided by the Intervention Mapping framework and MRC guidance for complex interventions, this four stage protocol includes: (1) Identifying psychological adaptation gaps through literature review and expert consultation; (2) a mixed-methods needs assessment; (3) intervention refinement via focus groups and e-Delphi; and (4) a pilot cluster-randomized controlled trial (N=88) in a tertiary care Pakistani pediatric oncology unit.

Results: The protocol will produce a manualized, stage matched intervention modified to the local cultural and healthcare context. Feasibility, acceptability, and preliminary efficacy will be evaluated.

Conclusion: This protocol addresses a critical gap in supportive care for caregivers in low resource settings. If successful, the intervention will provide an evidence-based, scalable tool for integration into routine oncology care in Pakistan.

Key words: Parent caregivers, psychological adaptation, childhood leukemia, Stage matched intervention, intervention development, Pakistan

Introduction

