Focus group and Delphi	To elicit comments on the model stage-matched intervention.	Parent caregivers will be engaged in focus groups to give their opinions on the model intervention developed from integrated information from earlier stages. Professionals	Delphi will be e-Delphi, and focus groups will be at participating tertiary care facilities.	As with the first interview, transcription and content analysis of discussions will be done. Expert opinion will be analysed using two indicators: the degree of concentration and coordination

		(psychologists, oncologists, nurses) will give feedback through the Delphi process.		of experts' opinions.
Pilot RCT of Draft Intervention	To test the stage-matched psychological adaptation intervention for parent caregivers of children with leukemia in Pakistan.	A stage-matched intervention lasting 12 weeks with assessments conducted at baseline, mid-intervention, and end of intervention. 34 parent caregivers from each of the two study facilities (total N = 68).	A tertiary care hospital in Pakistan	Qualitative data will be transcribed and analysed. Two-tailed t-tests will be run for parametric quantitative data using 95% confidence intervals. Hedges' g formula, will be used to calculate effect sizes. Feasibility and acceptance will be measured by participants' ratings of the intervention's overall helpfulness. Baseline, midway, and post-intervention psychological adaptation and distress outcomes assessments will inform the program's initial efficacy.

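### The allowance for 25% attrition multiplies by 1.25 instead of dividing by 0.75, so 88 recruits leave about 66, not the implied 70; Table 3 separately gives the pilot as 68

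*Protocol*

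**What the plan says.** The size of the Stage 4 pilot appears in three places in the protocol.

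- **Section 2.10, Sample size:** "We aim to recruit $N = 70$ parent caregivers (35 per arm"). The precision claim follows: "This sample size allows estimation of a 75% retention rate with a 95% confidence interval width of $\pm 13"%. Then comes the allowance for loss: "Accounting for an anticipated 25% attrition rate common in LMIC psychosocial trials, we will recruit up to 88 participants".
- **Abstract, Methods:** "a pilot cluster-randomized controlled trial (N=88").
- **Table 3, row for the pilot RCT:** "34 parent caregivers from each of the two study facilities (total N = 68").

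Allocation is by facility, with one facility per arm: "each facility will be randomly assigned to either the intervention or control group". Just before the sample-size paragraph, section 2.10 also remarks: "The sample size estimation was initially derived using individual-level power calculations". The justification that follows rests on the precision of feasibility estimates, published advice on pilot size and comparable pilots.

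**The concern.** There are two separate faults.

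The first is the attrition step. A number is raised to allow for loss so that the starting number is still there at the end. Raising 70 to 88 for a 25% loss does not do this, because 25% of 88 is 22 and 88 − 22 = 66. Under the protocol's own attrition assumption, the 35 per arm is not reached.

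The second is Table 3. It describes the same pilot, with the same two facilities, but gives a total 20 below the abstract. Recruitment and retention rates are feasibility outcomes of this pilot, so the planned number is the reference for judging recruitment. It should be the same wherever it appears. The detailed pilot protocol announced in section 2.10 is also likely to take its figures from this document.

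**Working it through.** **Inputs.** Base N = 70, 35 per arm (section 2.10). Attrition d = 0.25 (section 2.10). Stated recruitment 88 (section 2.10 and abstract). Table 3 total 68, 34 per facility. Retention 75% with ±13% (section 2.10). One facility per arm; equal arms are taken from the 35 per arm.

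**1. Reproducing the stated 88.** N × (1 + d) = 70 × 1.25 = 87.5, so 88. Per arm, 35 × 1.25 = 43.75, so 44, total 88. This form gives the protocol's figure.

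**2. The inflation that keeps 70.** N / (1 − d) = 70 / 0.75 = 93.3, so 94. Per arm, 35 / 0.75 = 46.7, so 47, total 94. The stated figure is 6 short.

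**3. What 88 delivers.** 88 × 0.75 = 66, or 33 per arm. For 70 of 88 to remain, attrition may be at most 1 − 70/88 = 20.5%.

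**4. Whether 68 can be linked to the other figures.** Inflating 68 for 25% loss gives 68 / 0.75 = 90.7, so 91, or 68 × 1.25 = 85 by the form in step 1. Neither is 88. Going the other way, 88 × 0.75 = 66 and 70 × 0.75 = 52.5. None of these gives 68, so it follows from neither 70 nor 88.

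**5. Effect of the inflation error on precision.** For a between-arm mean difference in SD units, ignoring clustering, the 95% half-width is 1.96 × √(2/n per arm):

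- n = 35: 1.96 × √(2/35) = 0.47 SD
- n = 33: 1.96 × √(2/33) = 0.48 SD

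**6. The retention precision sentence.** The denominator of a retention rate is the number enrolled. The simple binomial half-width is 1.96 × √(0.75 × 0.25 / n):

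| n | Reading | 95% half-width |
|---|---|---|
| 35 | one arm of 70 | ±14.3% |
| 44 | one arm of 88 | ±12.8% |
| 70 | the N the sentence refers to | ±10.1% |
| 88 | all enrolled | ±9.0% |

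The stated ±13% does not reproduce at 70. It needs n = 1.96² × 0.1875 / 0.13² = 42.6, so about 43, which is close to one arm of 88. The protocol does not say that one arm is meant.

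**The case against.** Several points on the other side are sound.

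- **The protocol does not call 70 the number of completers.** It words 70 as a number to recruit. That 70 is the number to be retained is implied by the inflation step. The inference is reasonable, since raising 70 for attrition has no purpose if 70 is simply the number enrolled, but it remains an inference.
- **A reader might infer that sites face three rival stopping points: 68, 70 and 88.** The documents do not support that. Section 2.10 links 70 and 88 as the figures before and after attrition, and the abstract repeats 88. Only the 68 in Table 3 is unexplained.
- **A reader might infer that the shortfall undermines the pilot.** It does not. The Limitations section puts feasibility, acceptability and preliminary efficacy first and disclaims definitive testing. The precision of the retention rate depends on the number enrolled, and at both 70 and 88 it is better than the stated ±13%.
- **A reader might infer from the remark on power calculations that a hidden calculation contradicts the feasibility rationale.** The text says only that the size was initially derived that way, which may describe a step since replaced. The absence of its inputs here proves nothing.
- **Section 2.10 says the stage is described only briefly and that a separate pilot protocol will follow.** This lowers the urgency. It does not make the printed figures consistent.

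What remains untouched is that 88 is not the correct inflation of 70 for 25% loss, and that Table 3 contradicts section 2.10 and the abstract.

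**Conclusion.** Both faults stand, and they should be fixed without being treated as critical. At 25% attrition, 88 enrolled leave 66 (33 per arm), 4 fewer than the implied target; holding 70 would take 94. Table 3's total is 20 below the 88 given elsewhere, with no explanation, and this is the more visible inconsistency for anyone planning recruitment.

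The conclusion assumes equal arms, 25% loss in each, and 70 as the number meant to be retained. If 70 were instead the number enrolled, the step to 88 would have no basis, so the paragraph would still need correction. All the half-widths ignore clustering. With one facility per arm they do not describe the real uncertainty of a treatment effect and serve only to show that the inflation error by itself is small.

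**What to change.** Keep recruitment at 88 and correct the text around it.

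1. **Section 2.10:** state that 88 will be enrolled (44 per facility) and that, with 25% attrition, about 66 will complete (33 per arm). Stop presenting 70 (35 per arm) as the number that the inflation protects.
2. **Table 3:** change the pilot entry to 44 per facility, N = 88.
3. **Retention precision:** restate it for the enrolled number and name the denominator. At 75% retention, ignoring clustering, it is about ±9.0% for all 88 or ±12.8% for the 44 in one arm. Without this change, the sentence would lose the N it refers to once 70 is dropped, and a figure that does not reproduce would remain.
4. **Optional:** remove the remark on power calculations, since the stated rationale is feasibility. This is editorial.

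The cost is wording in section 2.10 and one table row, with no added participants. The expected number of completers becomes slightly less favourable, 66 instead of the implied 70.
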